11.1. Data Sets Analyzed

All heart failure patients with reduced ejection fraction that have a primary provider that has been randomized into the heart failure care delivery model intervention will be included in each analysis.

11.2. Demographic and Baseline Characteristics

The following demographic variables for each patient upon enrollment will be summarized: race, tribal affiliation, gender, age, BMI.

The following clinical variables and baseline characteristics will be summarized: most recent blood pressure and heart rate, baseline creatinine, baseline potassium, most recent brain

natriuretic peptide, if any heart failure hospitalization in last 12 months, ischemic or non-ischemic cardiomyopathy based on coexisting validated ICD for ischemic cardiomyopathy [ICD codes: ICD 9 414.8, ICD 10 I25.5]), comorbidities to include coronary artery disease, diabetes, chronic kidney disease (including stage, end-stage renal disease), atrial fibrillation, hypertension, hyperlipidemia, left ventricular ejection fraction on most recent echocardiography, and prior cardiac studies including coronary angiography, stress test, or cardiac MRI.

11.3. Analysis of Primary and Secondary Endpoints

To assess the effectiveness of our intervention, measurement of rates of GDMT, including each specific medication of ACE inhibitors, ARB, ARNI, beta-blockers, MRA, SGLT2 inhibitors will be performed at baseline, at each cross-over time point. The main analysis of our stepped wedge design will be based on a logistic mixed-effects model which will contain a random intercept to account for between-cluster variability, a fixed effect parameter for time, and a group indicator variable for the treatment for each subject and time to capture treatment differences over time.

Safety and tolerability data will be summarized by intervention group.

Adverse event rates will be coded by body system and MedDra classification term. Adverse events will be tabulated by treatment group and will include the number of patients for whom the event occurred, the rate of occurrence, and the severity and relationship to newly started therapy.

Statistical Analysis: The primary analysis will utilize the intention to treat principle. A generalized linear model will be used to assess the relationship between randomization cluster status and the primary outcome. The model will use a log-link and independent correlation structure to allow for calculation of adjusted risk ratios. Statistical significance will be based on a P value of <0.05. For categorical secondary outcomes, a similar generalized linear modeling approach will be used. For continuous secondary outcomes, a generalized linear model will be used.

Assessment of contamination: Providers may learn to better treat heart failure as consistent with evidence-based therapies over time. Given we are not clustering by provider, but rather patients, it is possible that providers will take what is being implemented on their patient that is in an active implementation phase, and apply it to a patient in a non-active implementation phase. Therefore, there is a high risk of contamination. However, with the stepped wedge design, we will be able to also see how GDMT rates increase over the study period for those clusters who are not immediately in an active implementation arm. We will be able to better understand if increases in GDMT are related to the intervention or just due to increases over time due to improved knowledge of providers over time.

Interim Analysis: We plan to have interim analyses at 30-days after enrollment of the first cohort. The interim analyses will allow us to stop the trial earlier for ethical considerations, unexpected adverse events. If there is high efficacy, we will continue the trial as all patients will be enrolled as per the stepped wedge design. Earlier stopping will be considered for the reason of safety and efficacy.

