4.3 Study Design

Stepped-wedge designs are increasingly being utilized to evaluate interventions within routine care and are recommended where there are limited numbers of clusters [13]. In this study, we will perform a prospective stepped-wedge randomized control trial, where randomization will occur at the patient level with 5 patient clusters.

The randomization procedures will be managed independently at the University of Pennsylvania Cardiovascular Outcomes, Quality, and Evaluative Research Center. Physicians will be randomized through a SAS-based computer-generated randomization scheme developed by the study PI. Using a stepped-wedge design, each patient cluster will begin the study as a control

site, providing treatment as usual to participants (Control). Clusters will then progressively commence the heart failure care delivery model and will begin contributing to the intervention arm of the study in a stepped fashion (Intervention; see **Figure 1**). An independent statistician at University of Pennsylvania Cardiovascular Outcomes, Quality, and Evaluative Research Center will randomly generate the clusters and the order of the patient cluster. CONSORT procedures will be followed including using an intention to treat analysis.

Figure 1: Stepped-Wedge Implementation of HF Care Delivery Model

Stepped Wedge Design

[figure not shown]

Figure 1. Stepped wedge randomized controlled study design. Participants in the control condition will receive treatment as usual. Participants in the intervention condition will receive the heart failure care delivery model as described below. The patient clusters and order of intervention will be randomly allocated.

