4.4. Randomization

Randomization in this study will occur at the level of the patient. This is a stepped wedge trial design, and patients will be randomized to 1 of 5 clusters. Every cluster will have the model implemented, but the time point of implementation will vary based on cluster, in 30 day increments. Cluster 1 will have the model implemented at time 0, cluster 2 at 30 days, cluster 3 at 60 days, etc (as shown in Figure 1). Prior to implementation, patients in pre-implementation time points will receive usual care. In addition, all providers received a lecture regarding updated ACC/AHA/HFSA guidelines and expert consensus prior to implementation of the model. Given the stepped-wedge design, all patients will eventually benefit from implementation of the model, but it also allows us to evaluate the effect of secular trends towards better care over time (and ensure the model rather than trends in care are not responsible for improving care).

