9 STUDY PROCEDURES AND GUIDELINES

9.1 Clinical Assessments

9.1.1. Baseline Medications

All baseline medications and their doses will be documented at enrollment of a patient's physician, as well as at each assessment cross-over time point. Dose, route, unit frequency of administration, will be captured. We only consider a patient to be on a medication if they have an filled prescription for the medication.

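### Class-by-class prescription status is repeated on individually randomised patients, but neither model in section 11.3 names the patient as the unit of correlation; the main model is then conservative and less precise, not prone to false positives

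*Combined protocol and SAP*

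**What the plan says.** Section 4.4 states: "Randomization in this study will occur at the level of the patient". Under section 4.3 an independent statistician "will randomly generate the clusters and the order of the patient cluster", so the clusters are start-time groups made by the randomisation, not clinics or providers. Section 11.3 agrees: "Given we are not clustering by provider, but rather patients". Section 9.1.1 records each patient's medications at enrolment "as well as at each assessment cross-over time point", and section 11.3 measures each class at baseline and at every cross-over.

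Section 11.3 describes two models. The first, which it labels the main analysis and which is the only one in the synopsis under the primary analysis plan, is a logistic mixed model with "a random intercept to account for between-cluster variability, a fixed effect parameter for time" and a treatment indicator. Subject appears there only as an index of that indicator. Of the second it says: "A generalized linear model will be used to assess the relationship between randomization cluster status and the primary outcome". It continues: "The model will use a log-link and independent correlation structure to allow for calculation of adjusted risk ratios". It then adds: "For categorical secondary outcomes, a similar generalized linear modeling approach will be used". The class percentages are categorical secondary outcomes under section 5.2, so both models can claim them.

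Section 11.4 makes the per-class rates the outcomes of interest and bases power mainly on SGLT2 inhibitors and ARNI. No section gives a patient random effect, grouping by patient, or a within-patient correlation.

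**The concern.** A patient who fills a prescription one month tends to fill it the next, so the repeated class records on one patient are correlated. An intercept for groups formed at random captures only the average of about 20 patients' stable differences; the rest stays in the residual. An independence model ignores the correlation unless its variance is corrected by patient.

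At stake are the standard errors, p-values and confidence intervals for the outcomes that power the trial. The direction of the error depends on choices that the text leaves open, so it has to be worked out for each model.

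**Working it through.** **Inputs.** From section 11.4: 20 patients per group, 4 groups, 5 time points with one baseline, 25% to 50%, 5% error (two-sided assumed). From section 4.1: 5 groups. I call the section 11.4 layout 4×5, and five groups with a baseline plus five measurements 5×6 (my assumption). Within-patient correlation ρ is assumed at 0.2 / 0.5 / 0.8.

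**1. The plan's own power.** Treat all 4 × 20 × 5 = 400 patient-periods as independent, with period effects. The period-adjusted treatment indicator has sum of squares 2.5 over the group-by-period cells. SE = √(0.375 × 0.625 / (20 × 2.5)) = 0.0685, and power = Φ(0.25/0.0685 − 1.96) = 95.5%. This matches the stated figure. Section 11.4 does not give its method, and other inputs also fit (control-rate variance with a group ICC of 0.01 gives 95.6%).

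**2. Independence model, model-based SE.** On the linear scale, true/reported variance = 1 − ρ + ρ·ΣS²/Q. S is each group's sum of the centred treatment indicator and Q is its total sum of squares. For 4×5, S = 1.5, 0.5, −0.5, −1.5, so ΣS² = 5, with Q = 5 without period terms and 2.5 with them. For 5×6, S = 2, 1, 0, −1, −2, so ΣS² = 10, with Q = 7.5 and 4. The false-positive rate is 2[1 − Φ(1.96/√ratio)]. Simulated values are for the log-link model with no time trend, 1000 trials each (Monte Carlo error 0.7 points at 5%).

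| Layout | Ratio | Closed form, % | Simulated, % |
|---|---|---|---|
| 4×5, no time term (as written) | 1.00 | 5.0 / 5.0 / 5.0 | 4.2 / 4.4 / 3.9 |
| 5×6, no time term (as written) | 1 + ρ/3 | 5.8 / 7.0 / 8.2 | 5.6 / 6.2 / 7.8 |
| 4×5, period terms added | 1 + ρ | 7.4 / 11.0 / 14.4 | 7.1 / 9.8 / 14.5 |
| 5×6, period terms added | 1 + 1.5ρ | 8.6 / 13.8 / 18.6 | 8.3 / 12.2 / 19.7 |

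With robust SEs clustered by patient, simulated error is 4.0 to 5.9% (4.2 to 7.0% in a separate run with a logit link).

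**3. Main model, group intercept only.** Stable patient differences create a between-group variance of ρ/20 of the total, which the intercept absorbs. The model treats the remainder as independent noise, although the true noise about each patient's level is only 1 − ρ of the total. With the group variance taken as known, true/reported variance is 0.83 / 0.57 / 0.28, so error is 2[1 − Φ(1.96/√ratio)] = about 3% / 0.9% / 0.02%. Simulation with the group variance estimated gives 4.9–5.5% / 3.2–3.4% / 1.4–1.7%. A separate simulation with likelihood-ratio tests gives 2.2–2.3% at 0.5 and 0.2–0.5% at 0.8. The exact values depend on fitting; the direction does not. Compared with patient-level GEE, the true SE is 5 / 15 / 45% larger in simulation (5×6, 2-point monthly rise). Against the linear patient-level optimum, with group variance known, it is 0.1 / 2 / 11% larger.

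**4. Patient-level models.** Exchangeable GEE grouped by patient with small-sample-corrected SEs gives 4.5 to 5.7% in all settings with constant correlation. A patient random intercept gives 6.0 / 4.8 / 5.8% (5×6, rise). If correlation instead decays from 0.8 between adjacent months (5×6, no trend), the group intercept gives 1.7%, GEE 4.2% and the patient intercept 4.0%.

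**5. Power in the 4×5 layout** (simulated: 500 trials, Monte Carlo error about 1 point).

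| Analysis | Closed form, % | Simulated, % |
|---|---|---|
| Main model, group intercept | 92.6 / 93.8 / – | 93.6 / 93.2 / 93.2 |
| Patient correlation modelled | 94.9 / 98.8 / >99.9 | 96.0 / 98.2 / 99.8 |
| Independence, period terms, patient-robust SE | 91.5 / 84.7 / 77.7 | 92.0 / 82.2 / 72.8 |

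The first closed-form entries are Φ((0.25 − 1.96 × reported SE)/true SE): at 0.2, (0.25 − 1.96 × 0.0762)/0.0695 = 1.45; at 0.5, (0.25 − 1.96 × 0.0801)/0.0604 = 1.54. In the 5×6 layout, simulated power is at least 99.8% for the group-intercept model and for GEE, and 98.2 / 94.2 / 86.0% for the robust independence model with period terms.

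**6. Primary endpoint.** Simulated with no effect, period terms and assumed start and stop rates. Scored per 30-day interval, within-patient correlation is about zero and all models give 4 to 6%. Scored cumulatively from baseline over repeated rows, correlation is 0.62 to 0.70: the model-based independence GLM gives 16 to 17%, the robust version 4.5 to 6.0%, and the group-intercept model 2 to 5%. The ACEI/ARB-to-ARNI switch was not modelled.

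**The case against.** The documents favour the mixed model as the deciding analysis, and under it there is no inflation: the group intercept absorbs the shared part of the patient differences, and what remains is conservatism. That stands. It also stands that an independence working structure is the vocabulary of GEE, which is usually paired with robust variance, and that with patient-clustered robust SEs the second model holds its error rate. But the text states neither the clustering unit nor the variance, and that version loses power once period terms are added.

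A reader might infer that the plan carries a 12 to 20% false-positive risk. The documents do not support this: such rates need period terms that the log-link description does not list, together with model-based SEs that it does not state.

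Section 11 promises a detailed SAP before the final analysis, so some of this is detail still to come. However, the group-only random intercept is a stated choice, not an omission, and following it as written gives standard errors that are too wide at moderate or high correlation.

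**Conclusion.** The point holds for the repeated class-by-class outcomes. If ρ is between 0.2 and 0.8, the main model's false-positive rate runs from about nominal to 3% at 0.2, through about 1 to 3% at 0.5, to below 2% at 0.8, and its estimates are less precise than those of a patient-level analysis. In the section 11.4 layout, power is about 93% at ρ of 0.2 to 0.5, against the stated figure above 95% and about 95 to 99% with patient correlation modelled. The shortfall is about 2 points and does not appear in the five-group layout, so it would be wrong to read this as an underpowered trial. At 0.8 the estimate for the main model depends too much on how the group variance is fitted to rest a claim on.

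The independence model as written is nominal to about 8%. It reaches about 7 to 19% only with added period terms and model-based SEs. Leaving time out would also expose it to bias from a secular trend, a separate matter not counted here.

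A reader might also infer that the primary endpoint is compromised. Section 5.1 defines it at 30 days after implementation, which can be read as one value per patient; only cumulative scoring over repeated rows, which no section specifies, would bring it in. All non-nominal figures rest on the assumed correlation.

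**What to change.** In the SAP, designate one primary model for the repeated binary outcomes, with categorical period effects and the patient as the unit of correlation, and use the same structure for the categorical secondary outcomes. Two options are suitable:

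- GEE grouped by patient, exchangeable working correlation, robust SEs with a small-sample correction.
- A logistic model with a patient random intercept, reported as a patient-specific odds ratio. With a population-average log odds ratio of 1.10 (ln 3, for 25% to 50%), its simulated estimates were 1.47 / 2.44 / 6.48, and it needs careful numerical integration at high correlation.

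If the independence log-link model is kept for its risk ratios, add period terms, state that the variance is robust and clustered by patient, and accept the lower power shown above. State also whether an increase in therapies is scored from baseline, per 30-day interval, or once per patient.

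The cost is SAP wording, a patient identifier and a variance option in the model code. No new data or patients are needed.

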	mEq/L], hyperkalemia [K >5.5 mEq/L], AKI [defined as Cr increase >0.5 from baseline], Hyponatremia [Na<130 mg/dl], volume overload [urgent clinic visit/ ER visits for lower extremity edema, dyspnea, with clinical evaluation consistent with volume overload], hypotension (SBP <90mmHg), bradycardia (HR <50 bpm). Outcomes determined by review of medical, hospital, and billing records.
OTHER EVALUATIONS	None
SAFETY EVALUATIONS	Adverse events (to include hypokalemia [K<3.0 mEq/L], hyperkalemia [K >5.5 mEq/L], AKI [defined as Cr increase >0.5 from baseline], Hyponatremia [Na<130 mg/dl], volume overload [urgent clinic visit/ ER visits for lower extremity edema, dyspnea, with clinical evaluation consistent with volume overload], hypotension (SBP <90mmHg), bradycardia (HR <50 bpm).
PLANNED INTERIM ANALYSES	At 30-days after implementation for cluster 1, we will evaluate for safety. Serious adverse events will be monitored by the research team on an ongoing basis throughout the study.
STATISTICS Primary Analysis Plan	To assess the effectiveness of our intervention, measurement of rates of GDMT, including each specific medication of ACE inhibitors, ARB, ARNI, beta-blockers, MRA, SGLT2 inhibitors will be performed at baseline, at each cross-over time point, and at the conclusion of 6 months after the implementation of the intervention. The main analysis of our stepped wedge design will be based on a logistic mixed-effects model which will contain a random intercept to account for between-cluster variability, a fixed effect parameter for time, and a group indicator variable for the treatment for each subject and time to capture treatment differences over time.
Rationale for Number of Subjects	We anticipate there is approximately 100 patients with HFrEF actively engaged in care at GIMC. Our goal to enroll all patients given ethical concerns with withholding implementation to all patients.

SECTION 1: BACKGROUND

Statement of Purpose:

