4. STUDY DESIGN

4.1 Study Overview

This is a single ‘center’ (Gallup Service Unit- which includes two ambulatory clinics), stepped wedge cluster randomized design with 5 clusters planned. We will randomize each patient to 1 of 5 clusters, each of which has a different enrollment time point, separated 1 month apart. Each patient will receive intervention with the heart failure care delivery model at time of enrollment. Evaluations will be taken at each cross-over time point and at conclusion of 6 months. Screening data will be reviewed to determine subject eligibility. Subjects who meet all inclusion criteria and none of the exclusion criteria will be entered into the study. Prior to enrollment for each patient, a message will be sent in that patient’s chart through the EHR to the patient’s primary provider who has 7 days to opt out if they think patient should not be enrolled.

Probable Duration of Project: Total duration of subject participation will be 6 months.

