7.3 Control Condition- treatment as usual

Participants in the Control Condition will continue to receive medical treatment as usual as directed by their primary care physician. All physicians at THC and GIMC will receive a lecture at the start of the study on updated ACC/AHA/HFSA guidelines on optimal therapy for GDMT.

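### The main model has a single time parameter; read as a straight line and fitted to the all-treated 6-month readings, it would shift part of any curved usual-care trend into the treatment effect

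*Combined protocol and SAP*

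**What the plan says.** The synopsis (Primary Analysis Plan) and section 11.3 describe the same main analysis: a logistic mixed model with "a random intercept to account for between-cluster variability, a fixed effect parameter for time, and a group indicator variable for the treatment". Neither says whether time is a continuous slope or a set of period indicators.

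The reading schedule differs between places:
- Synopsis, immediately before the model: "at baseline, at each cross-over time point, and at the conclusion of 6 months after the implementation of the intervention".
- Section 11.3: "performed at baseline, at each cross-over time point", with no 6-month reading.
- Section 4.1: "Evaluations will be taken at each cross-over time point and at conclusion of 6 months", which could mean one common date.

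Section 4.4 sets the roll-out: "Cluster 1 will have the model implemented at time 0, cluster 2 at 30 days, cluster 3 at 60 days, etc". With the five clusters of section 4.1, starts fall on days 0, 30, 60, 90 and 120. The same section says of the design that "it also allows us to evaluate the effect of secular trends towards better care over time". Section 7.3 adds that "All physicians at THC and GIMC will receive a lecture at the start of the study", and section 11.3 expects provider learning and rates contamination as a high risk.

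**The concern.** In a stepped wedge the treated share rises with calendar time, so the treatment estimate is only as good as the time adjustment. An analyst following the singular wording literally would fit one slope. That does no harm under a null effect while readings are evenly spaced and the treated share climbs in equal steps. It stops being harmless once readings are added after the last cluster has crossed over. The treated share then sits at 100%, so it rises and levels off. A usual-care trend of the same shape cannot be absorbed by a straight line, and the treatment indicator picks up the remainder. At stake is the plan's claim that it can tell the care model's effect from general improvement in prescribing.

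**Working it through.** **1. The plan's own figure.** Section 11.4 claims more than 95% power for 25% against 50%, with four clusters, five time points and 20 patients per cluster. I used the Hussey-Hughes variance with categorical periods, two-sided 5% and ICC 0:
- Variance per cell: 0.375 × 0.625 / 20 = 0.01172.
- Design sums: U = 10, W = 0 + 1 + 4 + 9 + 16 = 30.
- Variance of the effect: 4 × 0.01172 / (4 × 10 − 30) = 0.00469; SE = 0.0685.
- Power: Φ(0.25/0.0685 − 1.96) = Φ(1.69) = 95.5%.

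The claim reproduces at ICC 0 (90.4% at ICC 0.01, 84.5% at 0.05). It cannot settle the coding. In that layout the treated share is 0, 25, 50, 75 and 100%, exactly linear in time, so a slope and period indicators give the same variance.

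**2. Where the 6-month readings fall.** At each cluster's own start plus 180 days they fall on days 180, 210, 240, 270 and 300. The last cluster starts on day 120, so none has an untreated comparison. Over the monthly readings on days 0 to 150 the treated share is 0, 20, 40, 60, 80 and 100%, a straight line. After that it is flat.

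**3. Large-sample bias under no effect.** The logistic model was fitted to expected proportions, with cluster variance at its two extremes (zero, and cluster fixed effects). Usual care was p(t) = 0.25 + d(1 − exp(−t/45)), with t in days. The 25% start is from section 11.4; the rise d and the 45-day constant are assumptions. Odds ratios with linear time:

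| Rise d | Cross-over readings only | Plus common day 180 | Plus own 6 months |
|---|---|---|---|
| 10 points | 1.00 | 1.02–1.03 | 1.08–1.11 |
| 20 points | 1.00 | 1.04–1.06 | 1.15–1.22 |

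The day-180 column takes monthly readings to day 150. Stopping them at day 120 moves its upper ends to 1.04 and 1.07. With one indicator per calendar occasion, every cell is 1.00.

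**4. Other trend shapes.** A trend linear on the logit scale gives 1.00 on every schedule. The accelerating rise p(t) = 0.25 + 0.15(t/300)² gives 0.94–0.95 with own 6-month readings, and another late-accelerating rise to 40% gave 0.83–0.88. The direction of bias therefore depends on the shape.

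**5. With a true effect.** For a true odds ratio of 3.0 (50% against 25%) and usual care rising to 40% by month 2, linear time gives about 3.4 to 3.5 with own 6-month readings and 3.09 to 3.15 with a common month 6. Categorical time returns 3.0.

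**6. False claims of benefit (nominal 2.5%).** Simulations used 100 patients, 1,500 runs per scenario and patient-clustered standard errors. Monte Carlo error is √(0.025 × 0.975/1500) = 0.4 points. With own 6-month readings:
- Rise of 10 points: 5.1% linear, 2.7% categorical.
- Rise of 20 points: 6.9% linear, 2.7% categorical.
- Rise to 40% by month 2: 5.7% linear, 3.0% categorical. Linear time gave 3.1% with a common month 6 and 2.5% with cross-over readings only.

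These concern use of one drug class, with assumed within-patient correlation. They do not use the planned mixed model with a cluster random intercept.

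**The case against.** The strongest reply is that the problem needs several conditions, none of which is written down. The text never says linear. Section 11.3 omits the 6-month reading, and on its schedule the null bias is nil. Section 1 describes a 6-month comparison with five 30-day steps, which fits a common end date and a much smaller bias. No section gives a trend shape. Section 4.4 places the lecture before implementation, so its effect may already be in the baseline. Section 11 also defers detail to a later SAP.

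Most of this stands, and it limits the point. A reader might infer that the plan definitely fits a straight line, that it forecasts a levelling-off trend, or that the error always favours the intervention. The documents support none of these: the coding is open, the expected drift has no stated shape, and an accelerating trend can bias the other way. A reader might also infer that the primary result is inflated. That has not been shown, because the primary endpoint is an increase in the number of therapies at 30 days, and the calculations concern prevalence of a single class.

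What does not stand is that nothing need be done. The singular wording appears twice. The synopsis lists the 6-month reading directly before the model. Its wording points to each cluster's own start, since a common day 180 would leave the fifth cluster only 180 − 120 = 60 days of follow-up. A later SAP may settle the coding, but section 11 requires it only before the final analysis, so the choice could be made with data in view.

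**Conclusion.** The point holds conditionally, as a free or cheap improvement. If time is one slope and the all-treated 6-month readings are pooled, a non-linear usual-care trend is partly assigned to treatment. For an assumed levelling-off rise of 10 to 20 points from 25%, the null odds ratio for one drug class is about 1.08 to 1.22 at own 6 months and about 1.02 to 1.06 at a common day 180. It is 1.00 if only cross-over readings are used. This is modest beside the odds ratio of 3.0 behind the sample size, but it affects the very separation of trend from effect that the design is meant to provide. The size rests on the assumed trend, the literal reading of the time term and the pooling of the late readings.

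**What to change.** In the synopsis and section 11.3, specify time as a categorical fixed effect for each calendar measurement occasion, in every model that estimates the treatment effect. That includes the log-link model in 11.3, for which no time term is listed. Define occasions by calendar date rather than visit label, so that own-6-month readings on different dates do not share one level.

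Reconcile the synopsis with sections 4.1 and 11.3: state whether the 6-month reading is at each cluster's own 6 months or on one common date, and whether it enters the effect model or only describes durability. Keeping it out of the effect model also removes the null bias.

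The cost is a change of wording and a slightly larger standard error. In the simulations the SD of the log odds ratio rose by at most about 3% (for example 0.319 against 0.317). The stated power is compatible with this coding at ICC 0.
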